9.14.2 Part 1 (SAD) Dosing Procedures in Cohort 5 (Healthy Volunteers)

Cohort 5 will receive the highest dose tested in subjects with mild or moderate hepatic impairment (Cohorts 1 to 4), and if any dose is confirmed to be a DLT during dosing of Cohorts 1 to 4, then that dose will not be studied in Cohort 5 of Part 1 (SAD).

9.14.3 Part 1 (SAD) Dose Escalation Procedures and Stopping Criteria for Subjects with Severe Hepatic Impairment (Group 3)

Group 3 severe hepatic impairment subjects will receive a single dose of NAL ER 27 mg. Group 3 dose stopping rules will take into account the DLT from the preceding Group 1 and Group 2 data.

If 2 subjects with mild or moderate hepatic impairment developed a DLT at the 27 mg dose, then that dose will be confirmed as DLT and will not be pursued in Group 3 subjects.

If 2 subjects with severe hepatic impairment develop a DLT, then the NAL ER 27 mg will not be dosed in the remaining Group 3 subjects (if not already dosed).

9.14.4 Part 2 (MAD) Dose Escalation Procedures and Stopping Criteria for Subjects with Mild and Moderate Hepatic Impairment (Group 1 and Group 2)

If 2 subjects develop a DLT at the same dose, then that dose will be confirmed as DLT.

If 2 subjects develop a DLT at 2 different doses (eg, 108 mg and 162 mg), then the higher of the 2 doses (162 mg in this example) will not be pursued in remaining Group 1 and Group 2 subjects (if not already dosed).

The maximum safe dose (MSD) will be determined as the dose level below the DLT dose.

Subjects who are currently receiving a confirmed DLT dose will not receive further dose of study drug. Subsequent subjects in Part 2 of the study will only be dosed through the completion of the MSD per the days specified in the titration table. After last dose, subjects will immediately enter the DLT Follow-Up Period (see [Section 9.11.1](#)).

9.14.5 PK Criteria Determination for Terminating the Study Following Part 1 (SAD) Safety Committee Review.

If in the judgement of the Safety Committee the Part 1 PK data demonstrates dose linearity across the dose range in both the mild and moderate hepatic impairment subjects (Group 1 and Group 2 subjects), such that PK modeling can be predictive of steady state dosing levels, a decision may be made to end the study without conducting Part 2 of the study.

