
	
If 2 subjects with severe hepatic impairment develop a DLT, then the NAL ER 27 mg will not be dosed in the remaining Group 3 subjects.
 
Part 2 (MAD) Dose Escalation Procedures and Stopping Criteria for Subjects with Mild and Moderate Hepatic Impairment (Group 1 and Group 2)
 
If 2 subjects develop a DLT at the same dose, then that dose will be confirmed as DLT.
 
If 2 subjects develop a DLT at 2 different doses (eg, 108 mg and 162 mg), then the higher of the 2 doses (162 mg in this example) will not be pursued in remaining Group 1 and Group 2 subjects (if not already dosed).
 
The study maximum safe dose (MSD) will be determined as the dose level below the DLT dose.
 
Subjects who are currently receiving a confirmed DLT dose will not receive further doses of study drug. Subsequent subjects in Part 2 of the study will only be dosed through the completion of the MSD per the days specified in the titration table. After last dose, subjects will immediately enter the DLT Follow-Up Period (see Section 9.11.1).

Discharge/Study Exit Procedures:	
Part 1 (SAD) on Day 4: brief physical examination, vital signs, body temperature, ECG, pulse oximetry, clinical chemistry, hematology, coagulation, urinalysis, PK sample, urine and serum pregnancy test (females only), and adverse events monitoring.
 
Part 2 (MAD) on Day 16: brief physical examination, vital signs, body temperature, ECG, pulse oximetry, clinical chemistry, hematology, coagulation, urinalysis, PK sample, urine and serum pregnancy test (females only), WI-NRS, and adverse events monitoring. On Day 17: PK sample.
 
In the case that a subject experiences a DLT or a DLT dose is confirmed in 2 subjects during Part 2 (MAD), post last-dose study procedures will be performed as laid out in the DLT Follow-Up Period (see Section 9.11.1). Early Termination procedures are only applicable to subjects who discontinue study drug for reasons other than those related to DLT.

Analytical Method:	
The Bioanalytical Division of Covance Labs will analyze nalbuphine and M1, M2, M4, and M5 metabolite concentrations (for select samples) in plasma using validated methods.

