9.11 Discharge/Study Exit Procedures

For Part 1 of the study, the following will be performed on Day 4: brief physical examination, vital signs, body temperature, ECG, pulse oximetry, clinical chemistry, hematology, coagulation, urinalysis, PK sample, urine and serum pregnancy test (females only), and adverse events monitoring.

For Part 2 of the study, the following will be performed on Day 16: brief physical examination, vital signs, body temperature, ECG, pulse oximetry, clinical chemistry, hematology, coagulation, urinalysis, PK sample, urine and serum pregnancy test (females only), WI-NRS, and adverse events monitoring. The following will be performed on Day 17: PK sample.

If not possible, all efforts will be made to complete study exit procedures within 14 days after the last participation of the subject in the study.

In the case that a subject experiences a DLT or a DLT dose is confirmed in 2 subjects during Part 2 (MAD), post last-dose study procedures will be performed as laid out in the DLT Follow-Up Period (see Section [9.11.1](#)). Early Termination procedures are only applicable to subjects who discontinue study drug for reasons other than those related to DLT.

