9.11.1 DLT Follow-Up Period for Part 2 (MAD), Post-Last Dose

In Part 2 of the study, any subject who experiences a DLT TEAE will not receive further dose of study drug, and safety follow-up procedures, per the DLT Follow-Up Period will be performed.

If 2 subjects develop a DLT, all subjects who are currently receiving a confirmed DLT dose will not receive further dose of study drug and will immediately enter into the DLT Follow-Up Period.

The maximum safe dose (MSD) will be determined as the dose level below the DLT dose.

Subsequent subjects in Part 2 of the study will only be dosed through the completion of the MSD per the days specified in the titration table. After dosing is complete, subjects will immediately enter the DLT Follow-Up Period and the following procedures will be performed:

DLT Follow-Up Period Procedures

- Subjects will be confined until after the 72-hour post-last dose blood draw and will come back for the final 96-hour post-last dose blood draw the following day at the Study Exit visit.
- Vital signs (blood pressure, heart rate, and respiratory rate): pre-last dose and approximately 1, 2, 4, 6, 8, and 12 hours post-last dose, and once a day until end of confinement.
- 12-lead ECG: pre-last dose and approximately 1, 2, 4, 6, 8, and 12 hours post-last dose and once a day until end of confinement.
- PK blood samples: a total of 12 blood samples will be collected for the last dose: at pre-last dose and 1.5, 3, 5, 7, 9, 12, 24, 36, 48, 72, and 96 hours post-last dose.
- Oxygen saturation via pulse oximetry will be measured: pre-last dose and at 1.5, 4.5, and 8 hours following the last dose (if morning dose), and at 2 hours following the last dose (if evening dose). Pulse oximetry measurements may be collected within 10 min before or after the specified time point. Oxygen saturation will be monitored via pulse continuous oximetry beginning at bedtime and continuing overnight until waking time through end of confinement with oxygen saturation measurements specifically recorded at approximately midnight and 4 am.
- WI-NRS will be performed on a daily basis, to be collected twice per day until end of confinement: once within an hour (+/- 1 hour) of completing their morning and evening meals, if applicable. Subjects will fill in the “Nighttime Itch” form in the morning and the “Daytime Itch” form in the evening.

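### In Part 2, two DLTs at two different doses drop the higher dose, but no mandatory rule stops a DLT-free subject who is already taking it

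*Protocol*

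**What the plan says.** Protocol Section 9.14.4 gives two rules for Part 2.

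- Same dose: "If 2 subjects develop a DLT at the same dose, then that dose will be confirmed as DLT".
- Two different doses, with 108 and 162 mg as the protocol's own example: the higher dose "will not be pursued in remaining Group 1 and Group 2 subjects (if not already dosed". Neither dose is called confirmed.

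The mandatory halt for subjects in mid-course follows: "Subjects who are currently receiving a confirmed DLT dose will not receive further dose of study drug". The Part 2 stopping rules in the synopsis say the same ("Subjects who are currently receiving a confirmed DLT dose will not receive further doses of study drug"). Section 9.11.1 repeats it with a broader opening but the same limit: "If 2 subjects develop a DLT, all subjects who are currently receiving a confirmed DLT dose will not receive further dose of study drug".

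The maximum safe dose (MSD) is defined once for both rules: "The maximum safe dose (MSD) will be determined as the dose level below the DLT dose". Section 9.14 adds an individual stop that covers only the subject who has the DLT. SAP Section 3.6 repeats the general rule from 9.14 and does not address the split case.

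**The concern.** The two-different-doses rule in 9.14.4 is worded as it is in 9.14.1 for Part 1. In Part 1 each level is a single dose, so exempting those already dosed exempts nobody who has drug still to come. In Part 2 each level is a run of doses. The same words then exempt subjects who are partway through the dropped level, and the mandatory halt does not reach them because no dose has been confirmed.

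At stake is a safety rule for hepatically impaired subjects on repeated dosing. The protocol treats a split pair of DLTs as enough reason to keep a dose from the remaining subjects. Read literally, it still lets those already on that dose carry on. A same-dose pair would stop them at once.

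**Working it through.** The plan states no figure for this rule, so the check is to apply the text to every case and count doses.

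**Inputs.** Dose levels 27, 54, 108 and 162 mg and the Part 2 titration table (Section 9.4); the two DLT rules, the halt and the MSD definition (9.14.4); the general DLT definition and the individual stop (9.14); the halt as repeated in 9.11.1.

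**Step 1: which pairs of DLTs trigger the halt.** Four levels give 4 × 5 / 2 = 10 unordered pairs of DLT doses.

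| Pair | Number | Dose confirmed? | Mandatory stop for DLT-free subjects on the (higher) dose? |
|---|---|---|---|
| Same dose (27/27, 54/54, 108/108, 162/162) | 4 | Yes | Yes |
| Different doses (27/54, 27/108, 27/162, 54/108, 54/162, 108/162) | 6 | No | No |

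The general definition in 9.14 does not change this. It needs the event in two subjects at one dose, and a split pair has one at each. The count of 6 in 10 is a count of rule cases, not a probability.

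**Step 2: how many doses a level contains.** Section 9.4 promises at least 5 consecutive doses per level; the titration table gives 6. At 162 mg: Day 10 evening (1), Day 11 (2), Day 12 (2), Day 13 morning (1), so 1 + 2 + 2 + 1 = 6. At 108 mg: Day 7 evening (1), Day 8 (2), Day 9 (2), Day 10 morning (1), again 6. Check on the whole table: 1 dose on Day 1, 11 × 2 = 22 on Days 2 to 12, and 1 on Day 13 make 24 = 4 × 6.

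**Step 3: doses still scheduled at the dropped level.** For a subject who has taken k doses of it, the remainder is 6 − k.

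| k | 1 | 2 | 3 | 4 | 5 | 6 |
|---|---|---|---|---|---|---|
| Doses left | 5 | 4 | 3 | 2 | 1 | 0 |

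The maximum is 5. If each k were equally likely, which is an assumption, the mean would be 15 / 6 = 2.5.

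**Step 4: what else could stop this subject.**

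- Section 9.13 permits, but does not require, withdrawal by the Sponsor or Investigator for safety.
- Section 9.14 lets the Investigator's concern stop escalation; it addresses a higher dose, not continued dosing at the current one.
- Section 9.4 lets the Safety Committee adjust doses or regimen, and makes each step up depend on how the previous level was tolerated.

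All of these are discretionary or concern moving up. None obliges anyone to stop a DLT-free subject at the dropped level.

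**The case against.** The strongest defence is that the rule is a graded response. In a split pair only one DLT occurred at the higher dose, and a single DLT at 162 mg never halts other subjects there. Starting nobody new while letting those who tolerate the dose finish is coherent. However, neither document states that intention. It also sits badly with a decision to drop the dose, and the wording matches a single-dose rule where the question cannot arise.

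The defence is also right that exposure is short and watched. These subjects are confined, with daily vital signs, pre-dose ECGs, daytime oximetry and continuous overnight oximetry, and any DLT of their own stops them at once. That limits the harm but does not supply the missing rule.

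Four stronger readings are tempting, and the documents do not support them.

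- **That nothing at all would stop the subject.** Discretionary stops exist; what is missing is a mandatory one.
- **That the MSD is a separate error.** The MSD sentence directly follows the split rule, 108 mg is the natural reading in the example, and later subjects are already kept off the dropped dose.
- **That follow-up is lost.** The trigger in 9.11 ("In the case that a subject experiences a DLT or a DLT dose is confirmed in 2 subjects during Part 2 (MAD") does not literally fit. But Early Termination is reserved for stops unrelated to DLT (9.11, 9.11.2), and 9.14.4 sends subjects to DLT Follow-Up after their last dose. The route can largely be inferred.
- **That the event has a calculable probability.** The documents give no DLT rates and do not state how Part 2 entry is staggered. Part 1 screens each dose before it enters Part 2. Any percentage would rest on invented inputs.

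**Conclusion.** The concern holds as a gap in a stated safety rule. After two DLTs at different doses in Part 2, a DLT-free subject partway through the higher dose is exempt from the drop and outside the mandatory halt. That subject could receive up to 5 further doses at the dropped level.

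This rests on the literal text of 9.14.4, 9.11.1 and the synopsis, and on the titration table being followed as printed. The broader opening of 9.11.1 may hint at a wider intent, but its halt still requires a confirmed dose. On likelihood, one can say only that the protocol itself foresees the 108/162 mg split, and that Part 2 may not be run at all (9.14.5). The text should be corrected before Part 2 starts.

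**What to change.** Add to 9.14.4 and 9.11.1, and align the Part 2 text of the synopsis:

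*In Part 2, subjects currently receiving a dose dropped under the two-different-doses rule will receive no further study drug and will enter the DLT Follow-Up Period; the MSD is then the next lower dose level.*

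Add the same case to the DLT Follow-Up trigger in 9.11 and the matching footnote of the Part 2 schedule of events. The MSD and follow-up wording are conforming clarifications. In the 108/162 mg example the MSD becomes 108 mg, a level at which one DLT occurred; the sponsor should accept that knowingly. The two-subject DLT definition in 9.14 can stay as it is.

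The change needs no new subjects or procedures. Its cost is information: halted subjects who were tolerating the dose lose the scheduled Day 13 steady-state profile. They keep a post-last-dose profile to 96 hours where feasible ("a total of 12 blood samples will be collected for the last dose"). It may follow an evening dose, lack the 8-hour fast required on Day 13, and precede steady state at that level.

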9.15 Adverse Events and Serious Adverse Events

The Investigator or designee and research site staff are responsible for the detection, documentation, classification, reporting, and follow-up of events meeting the definition of an AE or SAE. Spontaneously reported or observed AEs will be recorded throughout the study, beginning at the time the subject gives informed consent. Subjects will be monitored throughout confinement for AEs and AEs may be elicited using a nonleading question at the discretion of the clinical staff. Regardless of seriousness, intensity, or presumed relationship to IP, all AEs will be recorded in the source documentation from the time of first contact with the subject (eg, screening) until the end of the follow-up period of the study. AEs that occur after screening and prior to administration of the first dose of IP will be recorded in the source documentation as baseline medical history. All measures required for management of AEs will be recorded in the source documentation. Any SAE that occurs after screening and prior to administration of the first dose of IP will be reported to Syneos Health Safety and Pharmacovigilance by the Investigator or designee within 24 hours of learning of the event.

9.15.1 Definitions

9.15.1.1 Adverse Events

An AE is any untoward medical occurrence in a patient or clinical investigation subject administered a pharmaceutical product and may not necessarily have a causal relationship with the administered treatment. An AE can therefore be any unfavorable and unintended sign (including a clinically significant laboratory abnormality, for example), symptom, or disease temporally associated with the use of a medicinal (investigational) product, whether or not related to the medicinal (investigational) product. During the study, an AE can also occur outside the time that the investigational product(s) was given (eg, during a washout period).

Surgical procedures themselves are not AEs; they are therapeutic measures for conditions that require surgery. The condition for which the surgery is required may be an AE. Planned surgical measures permitted by the clinical study protocol and the condition(s) leading to these measures are not AEs.

Pre-existing conditions, diseases, or disorders are not considered AEs unless there is a change in intensity, frequency, or quality.

9.15.2 Serious Adverse Events and Serious Unexpected Adverse Events

An SAE is any untoward medical occurrence that at any dose:

- Results in death,

- Is life-threatening (at the time of the event),
- Requires inpatient hospitalization or prolongation of existing hospitalization,
- Results in persistent or significant disability/incapacity, or
- Is a congenital anomaly/birth defect.

Important medical events that may not result in death, be life-threatening, or require hospitalization may be considered a serious adverse drug experience when, based upon appropriate medical judgment, they may jeopardize the subject and may require medical or surgical intervention to prevent one of the outcomes listed in this definition. Examples of such medical events include allergic bronchospasm requiring intensive treatment in an emergency room or at home, blood dyscrasias or convulsions that do not result in inpatient hospitalization, or the development of drug dependency or drug abuse.

A serious and unexpected AE is an SAE that is not identified in nature, intensity, or frequency in the risk information set out in the Reference Safety Information section of the IB or on the label of the drug.

9.15.3 Clinical Laboratory Abnormalities and Other Abnormal Assessments

Abnormal laboratory findings (eg, from clinical chemistry, hematology, or urinalysis) and other abnormal assessments (eg, from vital signs or ECGs) judged as clinically significant by the Investigator or designee will be recorded as AEs or SAEs if they meet the definitions provided in Section 9.15.1. Furthermore, abnormal laboratory findings and other abnormal assessments present at baseline that significantly worsen following the start of the study (ie, become clinically significant) will be reported as AEs or SAEs. However, abnormal laboratory findings present at the start of the study that do not worsen will not be reported as AEs or SAEs.

The Investigator will exercise his or her medical and scientific judgment in deciding whether an abnormal laboratory finding or other abnormal assessment is clinically significant.

In the FDA E14 Clinical Evaluation of QT/QTc and Proarrhythmic Potential Guidance (2005), mention is made that ECG analysis is considered a fundamental component of the drug candidates safety database. As part of the safety analysis that may be undertaken in the event of an ECG related AE, source ECG strips may be reviewed and evaluated by the Sponsor and/or their delegate.

9.15.4 Evaluation of Adverse Events and Serious Adverse Events

The Investigator or designee is responsible for making an assessment as to the seriousness, intensity, causality, and outcome of an AE.

9.15.4.1 Classification of Adverse Event Intensity

For each recorded AE or SAE, the Investigator or designee must make an assessment of intensity, if possible, based on the Common Terminology Criteria for Adverse Events (CTCAE) version 4.03 or later (https://evs.nci.nih.gov/ftp1/CTCAE/CTCAE_4.03/CTCAE_4.03_2010-06-14_QuickReference_5x7.pdf).¹⁴ A determination of grading at the time of AE occurrence is required in order to monitor for DLTs and may be modified upon continued assessment. If there is insufficient information to determine intensity, the AE must still be reported.

The severity of an AE that cannot be termed and graded by the most current version of CTCAE will be categorized as follows ([Table 4](#)):

Table 4 Classification of Adverse Event Intensity

Classification	Definition
Grade 1	Mild; asymptomatic or mild symptoms; clinical or diagnostic observations only; intervention not indicated.
Grade 2	Moderate; minimal, local or noninvasive intervention indicated; limiting age-appropriate instrumental activities of daily living.
Grade 3	Severe or medically significant but not immediately life-threatening; hospitalization or prolongation of hospitalization indicated; disabling; limiting self-care activities of daily living.
Grade 4	Life-threatening consequences; urgent intervention indicated.
Grade 5	Death.

Source: National Cancer Institute Common Terminology Criteria for Adverse Events (version 4.03) available for download at: <https://evs.nci.nih.gov/ftp1/CTCAE/About.html>.

9.15.4.2 Classification of Adverse Event Causality

For each recorded AE or SAE, the Investigator or designee must make an assessment of causality based on the criteria in [Table 5](#) to determine the relationship between the AE and the Investigational Product (IP).

Table 5 Classification of Adverse Event Causality

Classification	Definition
Unrelated	The AE or SAE is judged to be clearly and incontrovertibly due only to extraneous causes (eg, disease, environment) and does not meet the criteria for IP relationship listed under probable, possible, or unlikely.
Unlikely	The AE or SAE is unlikely related to the IP, when the AE or SAE 
 • does not follow a reasonable temporal sequence from administration of the IP • may readily have been produced by the subject's clinical state, environmental, or toxic factors, or other modes of therapy administered to the subject • does not follow a known pattern of response to the IP • does not reappear or worsen when the IP is re-administered
Possible	The AE or SAE is possibly related to the IP, when the connection to the IP appears unlikely but cannot be ruled out with certainty. This causal relationship is assigned when the AE or SAE 
 • follows a reasonable temporal sequence from administration of the IP • may have been produced by the subject's clinical state, environmental, or toxic factors, or other modes of therapy administered to the subject • follows a pattern of response to the suspected IP
Probable	The AE or SAE is probably related to the IP, when the connection to IP can be made with a high degree of certainty. This causal relationship is assigned when the AE or SAE 
 • follows a reasonable temporal sequence from administration of the IP • cannot be reasonably explained by the known characteristics of the subject's clinical state, environmental, or toxic factors, or other modes of therapy administered to the subject • disappears or decreases upon cessation or reduction in dose (note that there are important exceptions when an AE or SAE does not disappear upon discontinuation of the IP, yet drug relatedness clearly exists, eg, bone marrow depression or tardive dyskinesias) • follows a known pattern of response to the suspected IP • reappears upon re-challenge

